API	The Application Programming Interface is a type of software interface offering a service to other pieces of software. The API can be electronically interfaced and perform analysis with data transferred from computer-based applications.
Case Report Form	Printed or electronic document designed to record protocol-required information on each participant in a clinical study.
Device	In this protocol, the Device refers to the Kintsugi Voice Device.
Device Operator	Individual who operates the Device.
Dropout	After consenting to participation in trial (and therefore enrolling), a study subject discontinues participation in the trial (e.g., due to lack of interest, medical condition,

	adverse event). Dropout may simply be lost to follow up.
DSM-5	Diagnostic and Statistical Manual of Mental Disorders, Fifth Edition; standard classification of mental disorders for clinicians for diagnosis of neurobehavioral and psychiatric disorders.
Endpoint	Key outcome measure in a clinical study.
GAD-7	General Anxiety Disorder-7, a widely used rating scale to measure the severity of anxiety based on participant responses to seven questions.
GCP	Good Clinical Practice.
Ground Truth	Data assumed to be correct by direct observation or measurement. In this study, the clinical Ground Truth involves the clinician evaluation via SCID.
ICF	Informed Consent Form is used to provide subjects with the information they need to make a decision to volunteer for a research study. ICF will include a summary of the research, potential risks, and potential benefits.
Indeterminate	The model does not have high confidence to classify the participant for depression and / or anxiety. Up to 20% of the results are expected to be indeterminate.
IRB	The Institutional Review Board is a group that has been formally designated to review and monitor biomedical research involving human subjects.
MDD	Major Depressive Disorder is a mood disorder that causes a persistent feeling of sadness and loss of interest. It affects how you feel, think, and behave and can lead to a variety of emotional and physical problems. Also called clinical depression.
ML	Machine Learning is the study of computer algorithms that can improve automatically through experience and by the use of data instead of being explicitly programmed. It is

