	seen as a part of artificial intelligence. Machine learning algorithms build a model based on sample data, known as training data, in order to make predictions or decisions without being explicitly programmed to do so.
Phonemes	Distinct units of sounds.
PHQ-9	Patient Health Questionnaire-9 is a widely used rating scale to measure the severity of depression based on participant responses to nine questions.
PI	A Principal Investigator is the individual responsible for supervising the conduct of the clinical investigation, including protecting the rights, safety, and welfare of participants in a clinical trial.
PII	Personally Identifiable Information. Any representation of information that permits the identity of an individual to whom the information applies to be reasonably inferred by either direct or indirect means.
SAE	A Serious Adverse Event is an adverse event that leads to death or serious deterioration in the health of the participant.
SCID	Structured Clinical Interview is a semistructured interview guide for making the major DSM-5 diagnoses.
Sensitivity	
Measure of the proportion of participants truly having clinically significant depression or clinically significant depression as verified by a clinician who are correctly identified by the Device as Positive for depression or anxiety (or True Positive Rate).
 
$Sensitivity = (True\ Positive) / (True\ Positive + False\ Negative)$

Specificity	
Measure of the proportion of participants truly not having depression or anxiety as verified by a clinician who is correctly identified by the Device as Negative for depression or anxiety (or True Negative Rate).
 
$Specificity = (True\ Negative) / (True\ Negative$

	+ False Positive)
Standard of care	Medical or psychological treatment guideline that specifies appropriate treatment based on scientific evidence and collaboration between medical and/or psychological professionals in the treatment of a given condition.
Study Survey	A web-based study survey that will be administered to study participants.

Background Information

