Major Depressive Disorder (MDD) is the leading cause of disability worldwide.^{1,2} Depression and anxiety disorders are among the most prevalent of all mental disorders.³ Approximately eight percent of adults in the United States reported having at least one major depressive episode and 18.1% of adults in the US have anxiety disorder.^{3,4} Depression and anxiety disorders are a frequent comorbidity for patients suffering from chronic medical diseases, such as diabetes, cancer, and inflammatory bowel disease.⁵⁻⁷ Multiple studies show a 2-3 fold increase in the cost of treating these chronic conditions, if their depression goes undiagnosed or untreated. Early detection of disorders is key to both better health and economic outcomes.⁸ Diagnosing depression and anxiety can be challenging since there is no current biomarker test used to detect the possible presence of these conditions. The PHQ-2 / PHQ-9 screener, which can either be self-administered or administered by a clinician, is the most commonly used diagnostic instrument. Even though the US Preventive Services Taskforce and the American Academy of Family Physicians recommend screening in individuals 12 and older,^{9,10} with the US primary care visit averaging 16 minutes, mental health screening is frequently skipped,¹¹ and only an estimated 4.2% of primary care patients are screened for these conditions.

The DSM-5, the standard classification of mental disorders used by mental health professionals in the US, has definitions for MDD and anxiety disorders. However, reliability of psychiatric diagnosis is still low, even among psychiatrists.¹² Because psychiatric diagnoses are often based on inferences derived from observation of patient behavior and patient self-reports, interrater reliability are moderate, typically ranging between kappa values of 0.4 to 0.6.¹³

Primary care clinicians provide the majority and an increasing percentage of mental health care.¹¹ If the agreement between psychiatrists, specialists trained specifically on mental health care is low - the expectation is that it will be even more challenging for primary care clinicians to diagnose depression and anxiety. According to a global Lancet study, the General Practitioners' sensitivity is 47.3%.¹⁴ Multiple studies describe the underdiagnosis of depression and anxiety, which is even more pronounced among the more medically disenfranchised demographic groups such as the elderly and racial minorities.¹⁵

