Once processed, vocal features are extracted from the audio and inputted into the neural network models. The software interprets the acquired signals using signal processing and an artificial neural network to quantitatively evaluate voice characteristics for presence of indicators correlated to depression and anxiety. The Kintsugi Voice Device then generates an output for signs of depression and anxiety which is displayed to the Device Operator. The Kintsugi Voice Device output will be positive for depression or negative for depression and positive for anxiety or negative for anxiety. The outcome can also be “uncertain” or within an “indeterminate range” if the Device cannot provide a high-confidence result.

Study Objectives

This study seeks to evaluate the ability of the Device to aid clinical assessment for depression and anxiety by comparing its output with the established diagnostic standard consisting of a diagnosis made by a specialist clinician based on DSM-5 criteria.

This is a prospective study of up to 100 subjects, ages ≥ 22 years of age.

We are striving for a 50%/50% split of subjects who have depression and/or anxiety and subjects who do not have depression and/or anxiety.

Study Endpoints

Effectiveness Endpoints

The primary endpoints of this study are to:

1. Determine the specificity and sensitivity of the Device in discriminating the presence of a significant depressive episode using the Structured Clinical Interview for DSM-5 Clinical Trial Version as the established diagnostic standard (“gold standard”)
2. Determine the specificity and sensitivity of the Device in discriminating the presence of a clinically significant anxiety state using the SCID-5-CT as the established diagnostic standard

The secondary endpoints of this study are:

- Measurement of the percentage of all adults for whom the Device provided no result
- Determine the specificity and sensitivity of the Device in discriminating the presence of a significant depressive episode compared to the PHQ-9
- Determine the specificity and sensitivity of the Device in discriminating the presence of a clinically significant anxiety state compared to the GAD-7

Safety Endpoints

Adverse events (AEs) and serious adverse events (SAEs) will be collected and reported from enrollment, which is determined by informed consent signature, through the completion of the study.

Study Duration

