The participant will be given access to the informed consent form. The informed consent form serves to ensure that participants understand the purpose of the study, assessments the participants will be asked to undertake as part of the study, the risks and benefits of participating, and the voluntary nature of their participation. The informed consent form will inform the participants that they will provide a recording of their voice and video as part of the study. The informed consent form will also inform the participants that their specialist SCID assessments conducted over a HIPAA-compliant video-conferencing platform will be recorded for the purposes of the study and research. A copy of the consent form will be provided to the participant after they consent. A clinical research coordinator will be available to answer participant questions about the study.

Randomization

The order in which the online survey and SCID assessment occur will be randomized. All participants will participate in investigational (Kintsugi Voice Device) and comparator assessments (SCID assessment, PHQ-9, and GAD-7).

Figure 2: Study Design Flow

A schematic of the study steps is illustrated in Figure 2.

Participants will be considered enrolled once they have signed the informed consent form.

Participants will receive instructions on completing our web-based Study Survey. If the audio sample from the SCID assessment is not scorable (e.g. poor microphone quality, insufficient length, excessive background noise), the participant may be asked to submit an additional audio sample. A clinical research team member will run the audio sample through the Device. Participants will fill out the PHQ-9 and GAD-7 questionnaires as part of the Study Survey. The Device output, PHQ-9, and GAD-7 results will not be shared with the clinicians. Similarly, the Device output, the PHQ-9, and GAD-7 results will not be shared with the participants.

Participants will complete a SCID assessment immediately after or immediately before the web-based Study Survey. A clinical research coordinator will be available to support the participant if they run into issues with the Study Survey.

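### Two secondary endpoints appear to use the self-rated PHQ-9 and GAD-7 as the reference for the Device's sensitivity and specificity, against the protocol's own definitions and with bias of unknown direction

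*Protocol*

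**What the plan says.** All endpoints are listed in the Protocol under Study Endpoints, Effectiveness Endpoints. The primary endpoint for depression is assessed "using the Structured Clinical Interview for DSM-5 Clinical Trial Version as the established diagnostic standard", and the one for anxiety uses the same interview in the same role. The second and third secondary endpoints read "Determine the specificity and sensitivity of the Device in discriminating the presence of a significant depressive episode compared to the PHQ-9" and "Determine the specificity and sensitivity of the Device in discriminating the presence of a clinically significant anxiety state compared to the GAD-7".

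The definitions table at the front of the Protocol bears on how these are read:

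- Ground Truth: "In this study, the clinical Ground Truth involves the clinician evaluation via SCID".
- Sensitivity and Specificity: both are defined by the participant's true status as confirmed by a clinician.
- PHQ-9: a "widely used rating scale to measure the severity of depression based on participant responses to nine questions". The GAD-7 is defined in the same manner for anxiety, with seven questions.

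Under Randomization, all participants are to undergo the Device and the "comparator assessments (SCID assessment, PHQ-9, and GAD-7"), so the three instruments are listed together as comparators. The survey and the SCID take place on the same day, one directly after the other. Background Information says of the depression questionnaire: "The PHQ-2 / PHQ-9 screener, which can either be self-administered or administered by a clinician, is the most commonly used diagnostic instrument".

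No listed endpoint scores the PHQ-9 or the GAD-7 against the SCID.

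**The concern.** Sensitivity and specificity need a reference that stands for the truth. The two secondary endpoints have the same form as the primary ones, with the questionnaire where the SCID stood. If that is what is meant, the protocol uses these two terms in a sense that its own definitions exclude, because a self-completed severity scale is not a clinician's verification.

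The practical cost is in interpretation. A disagreement between the Device and the PHQ-9 may be an error of the Device or of the questionnaire. An agreement may be both right or both wrong. The endpoint counts every disagreement as a Device error and every agreement as a Device success. The figure could be quoted as Device accuracy although it is not.

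The more informative comparison is within reach. The same people have the Device result, the questionnaire and the SCID, so one can ask how the Device and the questionnaire each perform against the SCID. The listed endpoints do not ask this.

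**Working it through.** The protocol gives no accuracy target or expected value for these endpoints, so there is no planned figure to reproduce. The check asks what the endpoint would show for a Device of known accuracy.

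**Inputs**

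- Prevalence *π* by SCID: 0.5. This is the target split in Study Objectives, which applies to depression and/or anxiety combined. The split per condition is not given, so 0.3 and 0.4 are also shown.
- Device against SCID: Se = Sp = 0.80, and a perfect Device as a benchmark (assumptions).
- Questionnaire against SCID: s = p = 0.85, with range 0.75 to 0.95 (assumptions).
- Dependence of Device and questionnaire errors given SCID status: none, or the largest possible positive dependence. The documents do not say which is nearer the truth.

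**Formulas**

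P(Q+) = πs + (1−π)(1−p).

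Apparent sensitivity = P(Device+, Q+) / P(Q+). Apparent specificity = P(Device−, Q−) / P(Q−).

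- Independent errors: P(Device+, Q+) = π·Se·s + (1−π)(1−Sp)(1−p).
- Maximum dependence: P(Device+, Q+) = π·min(Se, s) + (1−π)·min(1−Sp, 1−p).

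**Main case, π = 0.5, Device 0.80/0.80, questionnaire 0.85/0.85**

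- P(Q+) = 0.5×0.85 + 0.5×0.15 = 0.50.
- Independent: (0.5×0.80×0.85 + 0.5×0.20×0.15) / 0.50 = (0.340 + 0.015) / 0.50 = **0.71**.
- Maximum dependence: (0.5×0.80 + 0.5×0.15) / 0.50 = (0.400 + 0.075) / 0.50 = **0.95**.
- By symmetry the specificity is the same in each case. The true value is 0.80.

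**Range over questionnaire accuracy, π = 0.5 (sensitivity and specificity are equal)**

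| Questionnaire | Perfect Device | 0.80/0.80 Device, independent | 0.80/0.80 Device, maximum dependence |
|---|---|---|---|
| 0.75/0.75 | 0.75 | 0.65 | 0.95 |
| 0.85/0.85 | 0.85 | 0.71 | 0.95 |
| 0.95/0.95 | 0.95 | 0.77 | 0.85 |

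**Other prevalences, independent errors, questionnaire 0.85/0.85**

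- π = 0.4: P(Q+) = 0.34 + 0.09 = 0.43. A perfect Device shows sensitivity 0.34/0.43 = 0.79 and specificity 0.51/0.57 = 0.89. A 0.80/0.80 Device shows 0.29/0.43 = 0.67 and 0.42/0.57 = 0.74.
- π = 0.3: a 0.80/0.80 Device shows sensitivity 0.225/0.36 = 0.625 and specificity 0.485/0.64 = 0.758.

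The apparent figures therefore also move with prevalence, although the Device's own accuracy is held fixed.

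**Precision of the alternative**

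If Device and questionnaire are each scored against the SCID, the 95% half-width for the paired difference in sensitivity is about 1.96·√(d/n). Here d is the proportion of SCID-positive participants in whom the two disagree (assumed 0.20 to 0.30), and the true difference is taken as near zero.

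- n = 50: 1.96·√(0.20/50) = 0.12, and 1.96·√(0.30/50) = 0.15.
- n = 40, if 20% of results are indeterminate (the upper figure in the definitions table): 1.96·√(0.20/40) = 0.14, and 1.96·√(0.30/40) = 0.17.

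Fifty is half of the maximum of 100 participants. Because the target split combines both conditions, meeting it exactly would leave at most 50 positives for either one.

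**The case against.** **The phrase *compared to* is ambiguous.** The primary endpoints call the SCID a diagnostic standard, and the secondary endpoints give the questionnaires no such title. Together with the clinician-based definitions, this lends some support to another reading: the Device's accuracy is to be compared with the questionnaire's, both against the SCID. This stands, and the conflict with the definitions cannot be called certain. It does not remove the point, since on that reading the endpoint fails to state the comparison it intends. Either way it needs rewording.

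**The harm is not one-sided.** A reader might infer that questionnaire errors count against the Device. The documents do not support that. It follows only if errors are roughly independent given SCID status. Under Study Design and Procedures, the Device input is the participant's own speech about illness and treatment history, recorded on the day the same person completes the questionnaires. Shared errors are plausible, and they would flatter the Device.

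**The data for the better comparison exist.** A reader might also infer that the trial can never show how the Device compares with the questionnaires. That is too strong. All participants are to have all measures, and a statistical analysis plan that is not shown could add the analysis. What can be said is that no listed protocol endpoint makes the comparison.

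**The main objective is safe.** The stated aim is comparison with a specialist DSM-5 diagnosis, and the primary endpoints do that. Read beside them, a low secondary figure is easier to interpret. The protocol claims no superiority over questionnaires. All of this stands and limits the point to the secondary endpoints.

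**Conclusion.** The point holds for the second and third secondary endpoints, on their most natural reading. They place a self-rated scale in the reference position and call the result sensitivity and specificity, which the protocol's definitions tie to the SCID and to a clinician's verification.

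The figures would mix two sources of error, and the sign of the bias cannot be known from the endpoint itself. For a Device that is truly 80%/80%, the apparent value at 50% prevalence runs from 0.65 to 0.77 with independent errors and from 0.85 to 0.95 with maximum dependence, as questionnaire accuracy varies from 0.75 to 0.95. All these accuracies are assumptions. Maximum dependence is an extreme used to show that the sign can reverse, not a forecast.

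The primary endpoints are unaffected. The sponsor should make this correction, but it does not threaten the main result.

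**What to change.** Reword the second and third secondary endpoints in Study Endpoints, Effectiveness Endpoints:

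1. Estimate sensitivity and specificity of the Device and of the PHQ-9 (depression) or the GAD-7 (anxiety), each against the SCID in the same participants. Report the paired difference with its confidence interval, as estimation only. The questionnaire cut-offs can be left to the statistical analysis plan.
2. If direct Device-versus-questionnaire results are still wanted, report them as positive and negative percent agreement, not as sensitivity and specificity.

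The cost is an endpoint amendment and a small added analysis of data already to be collected. There are two drawbacks. The Device may look no better than a questionnaire. Precision is also coarse: with 50 SCID-positive participants the interval for the difference in sensitivity is about ±0.12 to ±0.15 under the assumed discordance, and wider once indeterminate results are left out. For that reason the comparison should carry no formal claim.

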- An API that can be integrated into different clinical workflows. Input of the API is a patient voice sample that is at least 60 seconds
- Underlying machine learning algorithm that drives the Device outputs (“Algorithm”)
- Depression and Anxiety are separate algorithms

The Device output is the following:

- For depression:
 - The voice sample contains characteristics of depression (the model has high confidence that the speaker has depression),
 - The voice sample does not contain characteristics of depression (the model has high confidence that the speaker does not have depression),
 - Indeterminate (the model doesn’t have high confidence to classify the patient as depressed or not depressed)
- For anxiety:
 - The voice sample contains characteristics of anxiety (the model has high confidence that the speaker has anxiety),
 - The voice sample does not contain characteristics of anxiety (the model has high confidence that the speaker does not have anxiety),
 - Indeterminate (the model doesn’t have high confidence to classify the patient as anxious or not anxious)

Principles of Operation

[figure not shown]
The Kintsugi Voice Device technology is based on a large and growing body of research on voice biomarkers and their ability to detect and predict various neurological and mental disorders.^{16–18} Voice biomarkers are a set of acoustic features extracted from voice signals.¹⁹

Producing speech involves coordination of various cognitive and motor processes therefore samples of speech provide insight into the state of physical and mental health. Speech has

been studied for a variety of health conditions including dementia, aphasia, Parkinson’s, Alzheimer’s disease, and various psychiatric conditions.^{19–24}

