The study is expected to last up to 8 months. The duration of each individual subject’s involvement in the study will be approximately 2 hours total consisting of a screening call followed by a psychiatrist clinical evaluation and online survey. However, participants could be active on the study for up to 2 weeks to schedule a SCID assessment.

Study Design and Procedures

This is a prospective fully remote, decentralized clinical study to measure the sensitivity and specificity of the Device predictions against clinical ground truth for major depressive disorder and for generalized anxiety disorder. Up to 100 participants will undergo investigational and comparator assessments for major depressive disorder and a clinically significant anxiety state.

The research coordinator will schedule a time with the participant for the evaluation. There will be a two-part evaluation: a web-based study survey and a specialist clinician evaluation via the SCID assessment. The SCID assessment will include questions about the past medical history of the participant as well as questions from the Clinical Global Impression - Severity scale. The order of the two evaluations will be randomized to minimize any potential bias.

The Device output will be positive for depression, negative for depression, or indeterminate for depression and positive for anxiety, negative for anxiety, or indeterminate for anxiety. PHQ-9 and GAD-7 scores will also be collected through the Study Survey.

Participants will also be evaluated by a specialist clinician via the SCID assessment. The psychiatrist performing the SCID assessment will be a board-certified psychiatrist. The clinical evaluation via the SCID assessment will be recorded and the channel-separated audio file of the participant during this assessment will be used as the Device input. The input for the Device will be obtained by the clinical research team and will be at least one minute of audio taken from the SCID assessment where the participant is asked about their current illness history and treatment history. The results of these assessments will act as the clinical comparator for comparison with the Device output.

Clinicians and participants will both be blinded to the participant the Device output and the participant assessment results (SCID, PHQ-9, GAD-7). Further, a SCID reviewer may review the recorded SCID assessment and standard clinical assessment and completed SCID template to minimize interrater variability.

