Subject Identification and Recruitment, Process of Consent

Subjects may be recruited through various mediums including but not limited to social media, Craigslist, and/or specialized clinical trial recruitment groups. At the time of enrollment, the mental status of the participant will not be known. Subjects may be recruited from populations that self-select as interested in mental health. Potential subjects will be provided with detailed study information so that they are able to make an informed decision.

If subjects wish to enroll, they will need to answer brief pre-screening questions about the inclusion/exclusion criteria to determine if they meet the study inclusion/exclusion criteria. Subjects ineligible for the study will be told they do not qualify. Subjects eligible for the study will receive an informed consent form if they are interested in participating. Participant identity will be verified before enrollment.

Participants will then schedule a time for the SCID assessment and to take the web-based study survey within the same day. Study participants can choose to end participation in the study at any time. The clinical research coordinator will also answer any questions on the study that participants have prior to enrollment.

Participants will also provide basic information such as their physical address, emergency contact, age, and email. Only the necessary participant information and medical history required for the study will be collected.

Recruitment will continue until up to 100 participants have SCID results or until the Sponsor terminates the study. The Sponsor may collate interim results at any time during the study to determine whether the study should continue.

[figure not shown]
Process of Consent

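### The stretch of SCID audio fed to the Device is not fixed, and the staff who obtain it are not required to be masked to the reference results

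*Protocol*

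**What the plan says.** On the input, Study Design and Procedures has two consecutive sentences. The first says that "the channel-separated audio file of the participant during this assessment will be used as the Device input". The second says "The input for the Device will be obtained by the clinical research team and will be at least one minute of audio", taken from the part of the SCID "where the participant is asked about their current illness history and treatment history". The Study Device Description gives the matching technical floor: "Input of the API is a patient voice sample that is at least 60 seconds".

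On who handles it, the text below Figure 2 in the Randomization section says: "A clinical research team member will run the audio sample through the Device".

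On masking, Study Design and Procedures says: "Clinicians and participants will both be blinded to the participant the Device output and the participant assessment results (SCID, PHQ-9, GAD-7". The Randomization section adds: "The Device output, PHQ-9, and GAD-7 results will not be shared with the clinicians". It then withholds the same three items from participants. No other group is named.

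The primary endpoints are the sensitivity and specificity of the Device against the SCID, for depression and for anxiety separately.

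**The concern.** In a diagnostic accuracy study, the index test should be run in the same way on everyone, by people who do not know the reference result. The Protocol protects the other direction well: the psychiatrist does not see the Device output. The input side is less tightly written. The named part of a semistructured interview may hold several minutes of participant speech, and any stretch of a minute or more within it meets the Protocol. Two staff members who both follow the text could submit different audio for the same participant.

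If the person choosing also knew the SCID result, the choice could lean, even unintentionally, towards audio that agrees with it. An error of this kind would fall on the primary endpoints and would not show in a confidence interval.

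**Working it through.** **Step 1: what is fixed and what is open.**

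| Element of the Device input | Status in the Protocol |
|---|---|
| Recording | Fixed: SCID assessment |
| Speaker | Fixed: participant's separated channel |
| Topic | Fixed: present illness and past treatment |
| Minimum length | Fixed: one minute, equal to the Device's 60 seconds |
| Start point, maximum length, choice among eligible stretches | Not stated |
| Manual or scripted cut | Not stated |

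**Step 2: who is masked to what.**

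| Role | Required masking to SCID, PHQ-9 and GAD-7 |
|---|---|
| Clinicians, participants | Named in the blinding sentence |
| Staff who obtain the audio | None stated |
| Staff member who runs the Device | None stated |

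The Training and Monitoring section counts clinicians among research staff, so the boundary between the groups is not sharp. Even so, the audio and Device tasks go to the clinical research team, and the blinding sentence does not name that team.

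**Step 3: where a bias could enter.** The Device classifies automatically, so nobody interprets its output. That leaves the choice of audio.

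**Step 4: scale only.** The Protocol gives no figure to reproduce. Its inputs are up to 100 subjects, a target split of 50%/50% (Study Objectives) and up to 20% indeterminate results (definitions table). The split refers to depression and/or anxiety, so one condition alone may have fewer cases; 25 cases and 75 non-cases are assumed as the low end. It is also assumed that indeterminates leave the denominator and fall evenly.

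One participant whose classification changes between wrong and right moves the endpoint by 1/n. For context, the 95% half-width is 1.96 × √(p(1−p)/n), with p assumed to be 0.80 to 0.70.

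| n classified | Origin | 1/n (points) | 2/n (points) | Half-width (points) |
|---|---|---|---|---|
| 50 | 100 × 0.50 | 2.0 | 4.0 | 11.1–12.7 |
| 40 | 50 × 0.80 | 2.5 | 5.0 | 12.4–14.2 |
| 25 | assumed cases | 4.0 | 8.0 | 15.7–18.0 |
| 20 | 25 × 0.80 | 5.0 | 10.0 | 17.5–20.1 |
| 75 | 100 − 25 | 1.3 | 2.7 | 9.1–10.4 |
| 60 | 75 × 0.80 | 1.7 | 3.3 | 10.1–11.6 |

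One or two affected participants stay inside sampling error at every n shown. The table does not say how many would be affected.

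**The case against.** **The two input sentences do not really conflict.** This is right. A reader might infer two rival definitions, the whole file against an excerpt. Read in order, the first sentence names the recording and channel, and the second narrows it to a part and a minimum length. What stands is that the stretch within that part is left open.

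**The masking point is an absence.** Also right. Nothing says that the audio staff see any result, Figure 2 is not shown, and role separation may sit in study procedures not at hand. An unseen SAP is a weaker answer, because which audio is tested and under what masking is study conduct, which the Protocol already addresses in part.

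**Stronger readings that the text does not support.**
- A reader might infer that audio staff gain access to results from the sentence "The Sponsor may collate interim results at any time during the study to determine whether the study should continue", or from the clause in Data Collection and Storage on who may view study information. The first concerns the sponsor's decision to continue and the second confidentiality. Neither gives results to those who handle the audio.
- A reader might infer that an unwelcome or indeterminate output could prompt a new sample. The Protocol allows an additional sample only for unscorable audio, and its examples are all technical. The Device also has its own quality check, and indeterminate is a separate output.
- A reader might attach a bias figure. In a latent-normal simulation where someone who knows the label always keeps the better of two segments, with assumed true accuracy of 0.60 to 0.80 and assumed between-segment correlation of 0.5 to 0.95, apparent accuracy rises by about 4 to 16 points. That is what selection in every participant would do under invented inputs. It is no evidence that selection would occur.

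**Masking alone is not enough.** Fair. Anyone cutting by ear hears diagnostic content even when masked to the scores, so the uniform cut does most of the work.

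**Conclusion.** The point holds in a limited form. The Protocol fixes the source, speaker, topic and minimum length of the Device input, but not the stretch used, and it does not require the staff who obtain the audio and run the Device to be masked to the SCID, PHQ-9 and GAD-7 results. The choice of audio therefore remains discretionary, and it feeds the primary endpoints.

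Neither the size nor the direction of any bias can be derived. The step of 2.0 to 2.5 points per affected participant rests on the 50/50 target being met and, for the upper figure, on 20% indeterminates spread evenly. The wider range of 1.3 to 5.0 points rests on the assumed 25 to 50 cases of one condition. This is a cheap improvement to the design. It shows neither that staff are unmasked in practice nor that the results would be biased.

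**What to change.** 1. In Study Design and Procedures, define the input by one rule for every participant: all participant speech in the named part of the SCID, cut by timestamp or script. This suits a semistructured interview better than a fixed length from one point, which may not yield 60 seconds of participant speech. Align the preceding sentence with the rule. Also align the mention of a voice sample inside the Study Survey (end of the Randomization section), since Financial Considerations lists only PHQ-9 and GAD-7 there.
2. Extend the blinding sentence so that staff who extract the audio, judge whether it is scorable and run the Device are masked to SCID, PHQ-9 and GAD-7 results until the Device output is recorded.

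The cost is Protocol wording, a scripted or timestamped cut and role separation within existing staff. A few more no-result cases are possible. No visits or participants are added.
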